Subjects will be outpatients who meet the DSM-V criteria for PTSD (acute or chronic, confirmed by the Clinician Administered PTSD Scale [CAPS] and at least moderate severity, defined as score > 33 on the PTSD checklist [PCL-5]) and have at least moderate symptoms of depression (defined by moderate symptoms, or score ≥ 11 on the Quick Inventory for Depressive Symptomatology – Subject Rated [QIDS-SR]) and are 18 to 70 years of age (inclusive). Up to 35 participants will complete the study at the two sites, the Providence VAMC (Providence, RI) and the White River Junction VAMC (White River Junction, VT). Eligible subjects must provide written informed consent, be capable of comprehending the nature of the study, and be considered by the Investigator as likely to comply with the visit schedule. Additional inclusion/exclusion criteria are listed below.

2. Study Design

This study is a prospective, sham-controlled, trial of sTMS delivered to patients who are symptomatic despite ongoing pharmacotherapy for PTSD and mood symptoms. Serial self-report symptom assessments will take place at screening/baseline and weekly during the 4

weeks of the study. The treatment course will comprise a total of 20 double-blind treatment sessions. Treatments windows will be 10 calendar days to complete 5 treatments, with a 40-day window in total to complete 20 treatments. Post-treatment assessment sessions will take place on the last day of treatment, and again 1 month after the final treatment.

All veterans who complete the sham-controlled series will be offered open-label continuation treatment following the same administration structure (i.e., 20 open-label treatment sessions, with 10 calendar days to complete 5 treatments, within a 40-day window for all 20 treatments), with a 1-month, post-treatment visit). Of note, for patients who continue in open-label participation, the 1 final study visit (PT2, below) will occur 1 month after the final open label treatment.

3. Specific Procedures or Treatments

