A. Screening: Patients who call in response to advertisements for the study or are referred by clinicians and meet preliminary demographic eligibility criteria upon phone screen will be invited to the clinic for a screening visit. Participants will also be drawn from clinical and research clinics at participating sites. After providing written informed consent, psychiatric interview and self-report measures will be used to confirm eligibility with regard to diagnosis, past psychotropic treatment history, current health history, and current symptom severity. The requirement for maintenance on a stable regimen of psychotropic medications for 6 weeks prior to baseline and during participation in the course of sTMS will be discussed.

B. Baseline/First Treatment Day: Patients meeting eligibility criteria will return within 2 weeks to begin the treatment protocol. Consent will be reviewed and confirmed with standard-of-practice forms for each institution. If indicated, women will be given a pregnancy test to make sure they are not pregnant. Clinical assessments will be updated (if more than 2 weeks have passed since screening visit), and data regarding functioning and quality of life will be collected with standardized measures. sTMS delivery will be calibrated using standard NeoSync procedures found in the device's user manual.

C. Serial Assessments: In the table below, PT1 refers to the assessment after the final sTMS treatment (i.e., after week 4 of the sham-controlled phase and, if relevant, after week 8 of the open-label phase). PT2 refers to the assessment completed 1 month after the final treatment (sham-controlled or open-label). PT1 and PT2 will include a psychiatric interview with the study PI or their designee. SC= screening visit, BL=Baseline/first treatment day, OL = open-label, with brackets indicating procedures done only in patients participating in the OL continuation phase. End-of-treatment week assessments are listed according to number of weeks of sTMS therapy completed by the time of assessment. * Indicates repeat evaluation at baseline if more than two weeks has passed since screening. Note that psychiatric assessments will occur at SC/BL, PT1, [OL PT1,] and PT2.

Table 1: Serial Assessments

Abbrev:	Assessment Title:	Administered at:
CAPS	Clinician Administered PTSD Scale	SC, BL*, PT1, [OL PT1,] PT2
CTQ	Childhood Trauma Questionnaire	SC, BL*
CGI-S	Clinical Global Impression - Severity	SC, BL*, PT1, [OL PT1,] PT2

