QIDS-SR	Quick Inventory of Depressive Symptoms – Self Report	SC, BL*, Weeks 1-3, PT1, [OL Weeks 5-7, OL PT1,] PT2
PCL-5	PTSD Checklist	SC, BL*, Weeks 1-3, PT1, [OL Weeks 5-7, OL PT1,] PT2
GAD7	7 Item Generalized Anxiety Disorder Scale	SC, BL*, PT1, [OL PT1] PT2
Q-LES-	Quality of Life Enjoyment and Satisfaction	SC, BL*, PT1, [OL PT1] PT2
Q-SF	Questionnaire	
CGI-I	Clinical Global Impression – Improvement	PT1, [OL PT1,] PT2
PGI-I	Patient Global Impression - Improvement	PT1, [OL PT1,] PT2

D. sTMS Treatment Administration: sTMS will be delivered following NeoSync administration guidelines using the device user manual. Acting under the direct supervision of a TMS-credentialed physician, trained sTMS operators will supervise all treatments.

Treatment emergent side effects associated with stimulation (during treatments) and emerging between treatment sessions will be queried on each treatment day and recorded.

E. Serial Imaging: Participants (at Providence VAMC site) found eligible at SC may undergo three MRI scanning sessions during the course of this study. Scans may occur prior to BL/first treatment day and after completing each study phase (i.e., after PT1 and PT1 OL). Scans will be completed at Brown University MRI Facility (MRF) or Providence VAMC; with scanner location remaining consistent for each participant (i.e., a participant BL screened at Brown will undergo PT1 scan at Brown, not PVAMC). Eligible participants will be scheduled to arrive at either facility 1 hour prior to MRI start time. At that time research staff will review MRI safety and study procedures, and discuss any changes in mood, sleep, and/or medication since their last visit. Additionally, participants will be asked to complete the Perceived Stress Scale prior to entering the scanner. Once in the magnet, research staff will ensure that the participant is comfortable, able to view the task screen, and has been provided the necessary instructions regarding communication with research staff during the scan (e.g., using emergency squeeze ball). After each scan, the participant will be queried about their experience in the scanner to assess for anxiety and/or discomfort.

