We aim to maximize power through collaborative analyses including data collected from the two sites of the study. De-identified data will be shared for final analyses. At least 20 subjects will be completed in total. The sample size for this pilot controlled study is based on estimations regarding the appropriate amount of information required to inform next steps in trial design rather than on statistical significance calculations for any primary safety or efficacy endpoint. Previous studies of different TMS parameters for PTSD (without comorbid MDD) have utilized sample sizes of ~ N = 20. By employing a comparable sample size we anticipate having sufficient power to detect significant differences between baseline and endpoint. This sample size will be adequate to determine the appropriate sample size for a subsequent trial.

For the primary efficacy endpoint, we will analyze change in total scores on both PCL-5 scores from baseline to end point PT1. Categorical response (empirically defined as 50% decrease from pre-treatment baseline) and remission (below threshold score, per published standards for each scale) will be calculated for each scale, and these will be reported in a descriptive manner for the sample. Secondary efficacy endpoints will utilize pre- and post-treatment scores on the self-report scales and CAPS. Open-label results, potentially informing issues related to duration of treatment, will be reported descriptively.

IV. Material Inducements

Participants will be offered payments in the form of gift cards, for completion of three milestones in the study: \$25 giftcard for completion of all baseline procedures, \$25 giftcard for completion of all PT1 procedures, and \$50 giftcard for completion of PT2 procedures. There is a maximum total payment of \$100 to offset time and travel expenses incurred as a result of participation in the research assessments that are not standard of care for non-research patients who undergo sTMS therapy. Participants who undergo open-label treatment will receive an additional \$25 for completing OL PT1 procedures, bringing the maximum total of \$125

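### For participants who start on schedule, the screening PCL-5 that had to exceed 33 is also the baseline for the primary change score, so within-arm improvement includes some regression to the mean.

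*Combined protocol and SAP*

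**What the plan says.** - **Entry rule.** Section III.1 asks for "at least moderate severity, defined as score > 33 on the PTSD checklist [PCL-5". Section III.3.A places the eligibility check at the screening visit, where "psychiatric interview and self-report measures will be used to confirm eligibility with regard to diagnosis", treatment history and current symptom severity.
- **Timing.** Section III.3.B: "Patients meeting eligibility criteria will return within 2 weeks to begin the treatment protocol".
- **Schedule.** Table 1 in section III.3.C lists both PCL-5 and QIDS-SR at "SC, BL*, Weeks 1-3, PT1" and later visits. The asterisk "Indicates repeat evaluation at baseline if more than two weeks has passed since screening". Section III.3.B sets the same condition for updating the clinical assessments.
- **Analysis.** For the primary endpoint, section III.4 says "we will analyze change in total scores on both PCL-5 scores from baseline to end point PT1". Its power statement reads "we anticipate having sufficient power to detect significant differences between baseline and endpoint". It also says of the pilot: "This sample size will be adequate to determine the appropriate sample size for a subsequent trial". Response is defined as a 50% decrease from pre-treatment baseline and is reported descriptively. No active-versus-sham test is stated.

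**The concern.** The schedule and the timing rule work against each other. The repeat PCL-5 is triggered only by a delay that the protocol intends to avoid. Someone who starts on time therefore has a single pre-treatment PCL-5, and it had to exceed 33 for that person to be enrolled. Scores selected for being high are, on average, partly high by chance, and the next measurement falls back without any treatment effect. That fall counts as improvement in the change score.

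A late starter gets a re-measured baseline, so baseline means different things for different participants. The documents do not say whether the second score must pass the cut-off again.

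At stake is the contrast that section III.4 describes, baseline against endpoint. Its bias always runs towards apparent benefit. Read within an arm or over the whole sample, the pilot would overstate change, and it is meant to inform the size of a later trial.

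**Working it through.** There is no planned figure to reproduce. The minimum of 20 completers rests on information needs and comparison with earlier studies. No alpha, power, effect size or SD is given.

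**Inputs**
- From the documents: cut-off above 33 (section III.1), so 33.5 on a continuous scale; at least 20 completers (section III.4), up to 35 (sections III.1 and VI.1).
- Assumed, because the documents give none: PCL-5 mean μ of 30-50 and SD σ of 12-17 among those screened, and correlation r of 0.7-0.85 between screening and PT1. Scores are taken as bivariate normal with no treatment effect, and everyone as starting on schedule.

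**Step 1: expected fall.** With a = (33.5 − μ)/σ, the mean of those selected exceeds μ by σ·φ(a)/(1 − Φ(a)), and the expected fall is (1 − r) times that excess.

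Example, μ = 40, σ = 15: a = −0.433, φ(a) = 0.363, 1 − Φ(a) = 0.668. The ratio is 0.544 and the excess is 15 × 0.544 = 8.16, so the average eligible score is 48.2. The fall is 0.15 × 8.16 = 1.22 at r = 0.85 and 0.30 × 8.16 = 2.45 at r = 0.7.

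| μ | σ | Fall, r = 0.85 | Fall, r = 0.7 |
|---|---|---|---|
| 30 | 17 | 2.38 | 4.76 |
| 35 | 16 | 1.77 | 3.55 |
| 40 | 15 | 1.22 | 2.45 |
| 45 | 15 | 0.86 | 1.72 |
| 50 | 15 | 0.57 | 1.13 |
| 50 | 12 | 0.30 | 0.61 |

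In the first row 42% of those screened pass the cut-off; in the last, 92% do.

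**Step 2: effect on a paired test.** By simulation, a two-sided 0.05 paired test with no treatment effect should show significant improvement 2.5% of the time. With 20 analysed it does so in about:
- 4% at μ = 50, σ = 12, r = 0.85
- 9.5% at μ = 40, σ = 15, r = 0.85
- 15% at μ = 40, σ = 15, r = 0.7
- 37% at μ = 30, σ = 17, r = 0.7

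With 35 analysed, the two μ = 40 cases give about 14% and 24%.

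**Step 3: effect on 50% response.** This is the simulated response rate with the screening baseline minus the rate with a first-day baseline. With no true change it is 0.0 to 3.2 percentage points (0.032 × 35 = 1.1 participants at most). With a true 10-point fall it is 0.3 to 7.1 points (0.071 × 35 = 2.5 participants at most).

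**Step 4: what a fresh first-day baseline achieves.**
- If screening correlates equally with the first day and with PT1, both later scores have regressed by the same amount and the expected artefact is zero.
- If the correlation is 0.85 with the first day and 0.7 with PT1, then at μ = 40, σ = 15 the part left is 2.45 − 1.22, about 1.22 points, or half.
- If the cut-off is applied again to the fresh score, most of the artefact returns. At μ = 40, σ = 12, r = 0.8, a simulated fall of 1.17 points drops only to 0.76.

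In simulation with random allocation, the between-arm difference in change was zero apart from simulation error.

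**The case against.** **The trial is sham-controlled, so regression cancels between arms.** This is right for an active-versus-sham difference under random allocation, and it limits the harm. But section III.4 states no such test, its power statement concerns baseline against endpoint, and the documents do not describe how participants are allocated. The missing between-arm analysis is the larger gap; until it is filled, the exposed contrast is the one the plan describes.

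**A later sham-controlled trial would be sized on a between-arm difference and an SD.** This largely stands. A shift common to both arms would not alter the expected difference. The harm arises if within-arm change is used for sizing.

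**The size is assumed and the top of the range is unlikely.** This also stands. The 4.8-point figure needs a screened mean below the cut-off. Entrants must also have PTSD confirmed by CAPS and a CGI-S of moderately ill or worse, which points to a higher mean. With 20 participants, the 1.2 to 2.4 points at mean 40, SD 15 are no larger than one standard error of the mean change (about 1.8 to 2.5 points). Even so, they raise the false-improvement rate several-fold.

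**The cut-off and the baseline are not stated as firmly as the concern assumes.** Above 33 appears in section III.1 but not in the numbered inclusion list in section VI.1, which lets PTSD criteria be met at screening and/or baseline. No sentence defines the analysis baseline; it follows from the schedule, since no other pre-treatment PCL-5 is required of an on-time starter. This is a reason for clearer text and does not remove the problem.

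**Conclusion.** The concern holds. For participants who start within two weeks, the selection score doubles as the primary baseline, and within-arm PCL-5 change is biased towards improvement whenever the test-retest correlation is below 1. The expected size is 0.3 to 4.8 points over the assumed ranges, and 0.9 to 2.4 in the middle cases (mean 40 or 45, SD 15). The effect on 50% response is small with no true change and reaches about 7 percentage points in the extreme case with a true 10-point fall. All of this rests on assumed means, SDs and correlations, and the average would be smaller if many participants start late and are re-measured without a second cut-off. An active-versus-sham comparison under random allocation is not biased on average. This is a modest design weakness, worth correcting because the remedy is nearly free.

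**What to change.** - Remove the asterisk condition for PCL-5 and QIDS-SR in Table 1. Every participant completes both on the first treatment day, before session 1, and those scores are the analysis baseline.
- Keep eligibility on the screening score and state that the cut-off is not applied again.
- State the primary analysis as the active-versus-sham difference in PT1 PCL-5, adjusted for the first-day score (ANCOVA). Any regression left after the new baseline is then expected equally in both arms under random allocation.
- Report within-arm change and response as description only.

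The interview scales can keep the two-week rule to limit burden. CAPS and CGI-S are also tied to entry, so within-arm change on them keeps the same limitation and the report should say so.

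The cost is two short self-report forms for each on-schedule participant, at a visit that already takes place, with no extra visit.

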Potential participants will be recruited through advertisements in the community. Announcements to hospital and community clinicians will be made to facilitate referrals. Research assistants will provide preliminary screening with callers who express interest. Written informed consent will take place as described above, during the screening visit.

3. Potential Risks to Participants

A. Risk of side effects from sTMS treatments: The U.S. Food and Drug Administration has designated this device as a “non-significant risk device” in MDD patients, and in the largest sTMS trial to date for MDD, there were no statistically significant differences in side effects between active and sham sTMS (Leuchter et al., 2015). The most commonly side effect reported was headache (21.4% in active sTMS, 19.2% in sham sTMS). Over-the-counter pain medications such as acetaminophen or ibuprofen may be helpful for reducing discomfort associated with sTMS. Because sTMS remains investigational, study staff will assess subjects' well being and functioning before and after each treatment to minimize the risk of experiencing these or any other side effects.

B. Risk of Worsening PTSD/Depression Symptoms or Lack of Improvement: Risks associated with participation in this trial include possible lack of positive response to sTMS treatment. Worsening of PTSD/Depressive symptoms is also a risk. There is no guarantee that the treatment will lead to improvement of symptoms. During the course of sTMS treatments or after finishing the final session in an sTMS treatment series, symptoms may worsen. The research staff will evaluate subjects at every sTMS treatment session, and the study physician will be available at all times to ensure that participation in this research continues to be safe and reasonable for them.

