E. There may be other risks that are currently unknown. Although sTMS is a designated a non-significant risk device in an MDD population, the long-term effects of sTMS on individuals are not completely known. The research team will notify subjects if anything new is learned about the safety of sTMS that might make them change their mind about participating in this study.

3. Further Detail of Protection Against Risks

A. sTMS: A licensed study physician with experience and training in neuromodulation will be available throughout all sTMS sessions. Study technician (defined as a non-LIP) will be within the sTMS treatment area during all sTMS sessions. Spontaneous report of side effects of sTMS will be used to identify and address any sTMS-emergent adverse effects. Risk of other serious adverse events related to stimulation will be mitigated by careful screening of past health history, identification of underlying risk factors, and application of the study inclusion/exclusion criteria.

B. Confidentiality, privacy and security: Information about study subjects will be kept confidential and managed according to the requirements of the Health Insurance Portability and Accountability Act of 1996 (HIPAA). Those regulations require a signed subject authorization informing the subject of the following: What protected health information (PHI) will be collected from subjects in this study; Who will have access to that information and why; Who will use or disclose that information; The rights of a research subject to revoke their authorization for use of their PHI.

In the event that a subject revokes authorization to collect or use PHI, the Investigator, by regulation, retains the ability to use all information collected prior to the revocation of subject authorization. For subjects that have revoked authorization to collect or use PHI, attempts will be made to obtain permission to collect at least vital status (i.e. whether the subject is alive) at the end of their scheduled study period.

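### No side-effect query is scheduled after the last treatment day, so late non-psychiatric events, and events after the last session in early stoppers, rely on spontaneous report

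*Combined protocol and SAP*

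**What the plan says.** Aim i in Section I covers safety as well as efficacy. The checks that actively look for side effects are all attached to treatment:

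- Section III.3.D: effects that occur with stimulation and those "emerging between treatment sessions will be queried on each treatment day and recorded".
- Section VI.3.A (Potential Risks): "study staff will assess subjects' well being and functioning before and after each treatment".
- Section VI.3.B (Potential Risks): "The research staff will evaluate subjects at every sTMS treatment session".
- Section VI.5: clinic staff look for worsening and adverse events five days per treatment week.

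On timing, Section III.2 says: "Post-treatment assessment sessions will take place on the last day of treatment, and again 1 month after the final treatment". Table 1 and the text of Section III.3.C give PT2 the CAPS, CGI-S, QIDS-SR, PCL-5, GAD7, Q-LES-Q-SF, CGI-I and PGI-I, plus a psychiatric interview. Neither lists a side-effect or adverse-event item. For participants who go on to open-label treatment, PT2 comes one month after the last open-label session.

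Two other provisions bear on the point. Paragraph A of Further Detail of Protection Against Risks (Section VI) relies on spontaneous report to identify side effects and gives no end date. Section VI.6 has the site investigators report adverse events to the IRB and defines no collection window.

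**The concern.** A query on treatment days covers each interval between sessions, because the next session supplies the next question. It does not cover the interval after the last session. PT1 falls on the last treatment day, so it cannot pick up an event that begins after the participant leaves. PT2 comes late enough to do so, but it contains no such question.

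The same applies, sooner, to anyone who stops early. Their last treatment day is the last session they attended, and no early-termination contact is described. If poor tolerance is the reason for stopping, these are the participants whose later course matters most to a safety assessment.

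At stake is the completeness and comparability of the safety data in a pilot that has safety in its first aim and, under Aim iii, is meant to inform use of the device at home. The protocol itself says that "the long-term effects of sTMS on individuals are not completely known". Events found by asking and events found by waiting for the participant to mention them are not gathered on the same footing, so rates during and after treatment could not be compared directly.

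**Working it through.** The plan states no figure for a collection window, so there is none to reproduce. The check sets the provisions side by side and then measures the interval.

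**Step 1: what is scheduled, and when.**

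| Time | Scheduled side-effect query | Other scheduled assessment |
|---|---|---|
| Each treatment day, including the last (PT1) | Yes (III.3.D) | Checks around each session (VI.3.A, VI.3.B); scales at PT1 |
| First open-label day, continuers only | Yes, because it is a treatment day | None needed for this point |
| Last session to PT2 | None | None for all participants; optional MRI at one site |
| PT2 | None listed | Interview; symptom, function and global scales |
| After an early stop | None | No specific procedure described |

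**Step 2: which events fall in the gap.** Section VI.3.B warns: "During the course of sTMS treatments or after finishing the final session in an sTMS treatment series, symptoms may worsen". That passage concerns PTSD and depression symptoms. PT2 measures these with the CAPS, PCL-5, QIDS-SR and the global ratings, so this risk is covered. The events with no scheduled question are non-psychiatric ones. Headache is the example the protocol gives as the most common side effect (21.4% active, 19.2% sham in the earlier depression trial cited in Section VI.3.A). None of the listed scales is presented as a side-effect inventory.

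**Step 3: the length of the gap.**

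Inputs: 20 sessions, at 5 per week (Section VI.3.C), with a 40-day limit (Section III.2). PT2 is one month after the last session. Assumption: one month is 30 days.

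Formula: share of follow-up with no scheduled query = 30 / (treatment days + 30).

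- Shortest course: three full weeks plus five days, 3 × 7 + 5 = 26 days. Share = 30 / (26 + 30) = 30/56 = 54%.
- Four whole calendar weeks: 30 / (28 + 30) = 30/58 = 52%.
- Longest course: 30 / (40 + 30) = 30/70 = 43%.

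These are for a completer who does not continue. For a continuer, assuming the two courses run back to back with no gap:

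- 26 + 26 = 52 treatment days: 30 / (52 + 30) = 30/82 = 37%.
- 40 + 40 = 80 treatment days: 30 / (80 + 30) = 30/110 = 27%.

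For an early stopper, no query is scheduled at any time after the last session attended.

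**Step 4: the two methods.** Section III.3.D describes asking. Paragraph A of Further Detail of Protection Against Risks describes waiting for a report. During treatment both can operate. After the last session only the second remains.

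**The case against.** The strongest reply is that safety collection does not end at the last session. Spontaneous report has no stated end, adverse-event reporting to the IRB has none either, and an interviewer at PT2 may hear of an event. At one site, participants who have an MRI after PT1 are also asked about changes in mood, sleep and medication. This stands. A reader might infer that collection stops with treatment, and the documents do not support that: what ends is the scheduled, active query. The remaining routes do not replace it, however. Reporting to the IRB handles events already known, and neither the interview nor the optional scan visit is described as covering side effects.

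A reader might also infer that the plan ignores the worsening it warns of after the final session. It does not, because that warning is about psychiatric symptoms and PT2 measures them.

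A third inference would be that the open-label offer seriously biases ascertainment, since continuers are asked on their first open-label day about the time since blinded session 20 and decliners are not. The difference is real. But Table 1 numbers the open-label weeks from 5, which suggests that the second course follows directly, so the extra coverage for continuers is probably short. That PT2 comes after open-label treatment for continuers is inherent in offering the extension.

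On early stoppers, the text does not exclude them from PT2. If they attend, though, PT2 still contains no query.

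Finally, the pilot is not sized on any safety endpoint (Section III.4), so this is an inexpensive improvement to data collection and not a threat to the design.

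**Conclusion.** The point holds in a limited form. Scheduled active collection of side effects ends on the last treatment day. Late non-psychiatric events, and events after the last session in participants who stop early, depend on spontaneous report. No adverse-event collection window is stated, and the protocol describes two methods of ascertainment without saying which applies when.

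For a completer who does not continue, the interval with no scheduled query is 43% to 54% of follow-up. This assumes a 30-day month and a treatment course of 26 to 40 days. For continuers it is 27% to 37%, with the further assumption of no gap between phases. These are shares of calendar time. It would be tempting to conclude that recorded event rates will be too low by a similar amount, but the documents give no rate of delayed events, so neither the number missed nor any difference between arms can be estimated from them.

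**What to change.** 1. Add the treatment-day side-effect query, unchanged, to PT2, covering the time since it was last asked. PT1 and the first open-label day need no addition, because both are treatment days.
2. For participants who stop early, ask the same questions by phone or visit one month after the last session they attended.
3. State the adverse-event collection window, and reconcile Section III.3.D with paragraph A of Further Detail of Protection Against Risks, so that it is clear when side effects are asked about and when they are only volunteered.
4. For open-label continuers, report events recorded before the first open-label session with the blinded phase, and note that later events cannot be separated from open-label exposure. Continuers will then have a shorter blinded observation period than decliners, so give its length beside the counts.

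The cost is one amendment, a few minutes at a visit that is already scheduled and compensated (Section IV, Material Inducements), and one contact per early stopper. Reported event rates may be slightly higher as a result. Sample size and efficacy endpoints do not change.
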